2.3. Sample Size Considerations

The sample size of this first-in-human clinical study was selected with the goal of balancing between safety and tolerability considerations in dose escalation and obtaining sufficient initial information related to the safety and biological activities of BIIB105. Sample sizes of 6 participants receiving active treatment in lower dose Cohorts A and B will allow an █% or greater probability to observe at least 1 occurrence of an AE with event rates of █% or greater. The sample size of 9, 36, and 12 participants exposed to active doses in Cohorts C1, D1, and D2, respectively, allow an █% or greater probability to observe at least 1 occurrence of an AE with event rates of █%, █%, and █%, or greater, respectively.

Cohort C2 will expose 3 participants with polyQ-ALS to active treatment as part of additional dose escalation step specifically for participants with intermediate-repeat CAG expansions in *ATXN2* gene as they may be more sensitive to the effects of BIIB105. The sample size of 3 was selected solely as precaution step before exposing participants with polyQ-ALS to 120 mg dose of BIIB105 in Cohort D2.

The sample size of Cohort D1 provides approximately █% power to detect a █% difference in the ratio to baseline in plasma NfL, in the BIIB105 versus placebo group, based on Cohort D1 120 mg data (N on BIIB105 = 36) vs pooled placebo data across Cohorts A through D1 (N = 19), with 2-sided █% significance level, assuming █% SD in both groups.

Assuming approximately █% drop out rate, the combined sample size of Cohorts D1 and D2 provides approximately █% power to detect a █% difference in the ratio to baseline in plasma NfL in the BIIB105 versus placebo group, based on pooled Cohorts D1 and D2 120 mg data (N=39) vs pooled placebo data across all cohorts (N=23), with a 1-sided █% significance level, assuming █% SD in both groups.

3. Definitions

3.1. Dates and Points of Reference

[figure not shown]
- Study Day 1: the date of the first dose of study treatment
- Study Day
 - For a date on or after Study Day 1
Study Day = (Date of Interest) – (Study Day 1) +1
 - For a date before Study Day 1
Study Day = (Date of Interest) – (Study Day 1)
- Baseline: Unless stated otherwise, baseline data are defined as the last data collected prior to the time and/or on the date of first dose, which is usually the same day as the Day 1 Predose/Baseline Visit. If baseline data at Day 1 predose/Baseline visit are missing, the last non-missing data prior to dosing (including data from Screening) will be used as baseline. For PD biomarkers, if predose baseline data (Day 1 predose/baseline or screening data prior to dosing) are missing, the non-missing data collected within 24 hours after first dosing will be used as baseline.
- Data from Assessments at Early Terminated Visit and Unscheduled Visits:

CONFIDENTIAL

The information contained herein may not be used, disclosed, or published without the written consent of Biogen MA Inc.

[figure not shown]
Data from early termination visits and unscheduled visits will be assigned to an appropriate scheduled postbaseline visit using a windowing scheme for assessments that are tabulated or summarized by visit. Scheduled visits will not be windowed.

For [REDACTED] PD biomarkers, the analysis window will be defined based on the schematic as follows:

[figure not shown]
CONFIDENTIAL

The information contained herein may not be used, disclosed, or published without the written consent of
Biogen MA Inc.

[figure not shown]
CONFIDENTIAL

The information contained herein may not be used, disclosed, or published without the written consent of
Biogen MA Inc.

[figure not shown]
CONFIDENTIAL

The information contained herein may not be used, disclosed, or published without the written consent of
Biogen MA Inc.

[figure not shown]
[figure not shown]
CONFIDENTIAL

The information contained herein may not be used, disclosed, or published without the written consent of
Biogen MA Inc.

[figure not shown]
[figure not shown]
CONFIDENTIAL

The information contained herein may not be used, disclosed, or published without the written consent of
Biogen MA Inc.

CONFIDENTIAL

The information contained herein may not be used, disclosed, or published without the written consent of
Biogen MA Inc.

CONFIDENTIAL

The information contained herein may not be used, disclosed, or published without the written consent of
Biogen MA Inc.

[figure not shown]

Table 8 Analysis Visit Windows for CSF PK/PD data

Visit	Lower Bound (inclusive)	Upper Bound (inclusive)	Target Day	Cohort
Baseline ^(a)	Last record prior to dosing	Last record prior to dosing	1	All cohorts
Day 15 ^(a)	9	22	15	All cohorts
Day 29 ^(a)	23	43	29	All cohorts
Day 57 ^(a)	44	71	57	All cohorts

CONFIDENTIAL

The information contained herein may not be used, disclosed, or published without the written consent of
Biogen MA Inc.

Day 85 ^(a)	72	88	85	Cohorts A, B, C1, C2 only
Day 85 ^(a)	72	99	85	Cohorts D1, D2 only
Day 92	89	111	92	Cohorts A, B, C1, C2 only
Day 113	100	127	113	Cohorts D1, D2 only
Day 130	112	152	130	Cohorts A, B, C1, C2 only
Day 141	128	155	141	Cohorts D1, D2 only
Day 169	156	183	169	Cohorts D1, D2 participants who are dosed in Part 2 after Part 1 treatment period
Day 169	156	172	169	Cohorts D1, D2 participants who are not dosed in Part 2 after Part 1 treatment period
Day 175	153	189	175	Cohorts A, B, C1, C2 only
Day 176	173	195	176	Cohorts D1, D2 participants who are not dosed in Part 2 after Part 1 treatment period
Day 214	196	236	214	Cohorts D1, D2 participants who are not dosed in Part 2 after Part 1 treatment period
Day 259	237	273	259	Cohorts D1, D2 participants who are not dosed in Part 2 after Part 1 treatment period

CONFIDENTIAL

The information contained herein may not be used, disclosed, or published without the written consent of
 Biogen MA Inc.

Note: The lower bounds of visits are calculated as: target day - (target day – target day of previous visit)/2+1. The upper bounds of all visits are calculated as: target day + (target day of next visit – target day)/2 except for Day 175 for cohorts A, B, C1, and C2, which is calculated as: target day + 14, for Day 169 for cohorts D1, D2 participants who are dosed in Part 2 after Part 1 treatment period, and for Day 259 for cohorts D1, D2 participants who are not dosed in Part 2 after Part 1 treatment period, which is calculated as: target day + 14. Both lower and upper bounds are based on all cohort schedules.

(e) Common visits between Cohorts A, B, C1, C2, D1, and D2.

Table 9 Analysis Visit Windows for Plasma PD data

Visit	Lower Bound (inclusive)	Upper Bound (inclusive)	Target Day	Cohort
Baseline ^(a)	Last record prior to dosing	Last record prior to dosing	1	All cohorts
Day 29 ^(a)	16	43	29	All cohorts
Day 57 ^(a)	44	71	57	All cohorts
Day 85 ^(a)	72	107	85	Cohorts A, B, C1, C2 only
Day 85 ^(a)	72	99	85	Cohorts D1, D2 only
Day 113	100	127	113	Cohorts D1, D2 only
Day 130	108	152	130	Cohorts A, B, C1, C2 only
Day 141	128	155	141	Cohorts D1, D2 only
Day 169	156	183	169	Cohorts D1, D2 participants who are dosed in Part 2 after Part 1 treatment period
Day 169	156	191	169	Cohorts D1, D2 participants who are not dosed in Part 2 after Part 1 treatment period

CONFIDENTIAL

The information contained herein may not be used, disclosed, or published without the written consent of Biogen MA Inc.

Day 175	153	189	175	Cohorts A, B, C1, C2 only
Day 214	192	236	214	Cohorts D1, D2 participants who are not dosed in Part 2 after Part 1 treatment period
Day 259	237	273	259	Cohorts D1, D2 participants who are not dosed in Part 2 after Part 1 treatment period

Note: The lower bounds of visits are calculated as: target day - (target day – target day of previous visit)/2+1. The upper bounds of all visits are calculated as: target day + (target day of next visit – target day)/2 except for Day 175 for cohorts A, B, C1, and C2, which is calculated as: target day + 14, for Day 169 for cohorts D1, D2 participants who are dosed in Part 2 after Part 1 treatment period, and for Day 259 for cohorts D1, D2 participants who are not dosed in Part 2 after Part 1 treatment period, which is calculated as: target day + 14. Both lower and upper bounds are based on all cohort schedules.
 
(f) Common visits between Cohorts A, B, C1, C2, D1, and D2.
				

Table 10 Analysis Visit Windows for MMSE

Visit	Lower Bound (inclusive)	Upper Bound (inclusive)	Target Day	Cohort
Baseline ^(a)	Last record prior to dosing	Last record prior to dosing	1	All cohorts
Day 8 ^(a)	5	18	8	All cohorts
Day 29 ^(a)	19	43	29	All cohorts
Day 57 ^(a)	44	71	57	All cohorts
Day 85 ^(a)	72	99	85	All cohorts
Day 113	100	127	113	Cohorts D1, D2 only
Day 141	128	155	141	Cohorts D1, D2 only

CONFIDENTIAL

The information contained herein may not be used, disclosed, or published without the written consent of Biogen MA Inc.

Day 169	156	183	169	Cohorts D1, D2 only

Note: The lower bounds of visits are calculated as: target day - (target day – target day of previous visit)/2+1. The upper bounds of all visits are calculated as: target day + (target day of next visit – target day)/2 except for Day 175 for cohorts A, B, C1, and C2, which is calculated as: target day + 14, for Day 169 for cohorts D1, D2 participants, which is calculated as: target day + 14. Both lower and upper bounds are based on all cohort schedules.
 
(a) Common visits between Cohorts A, B, C1, C2, D1, and D2.
				

If more than one observation is within the same window, data from the regular scheduled visit will be used for that visit.

If neither of the observations are from a regular scheduled visit the observation closest to the target day will be used. However, if both the observations are equally distant from the target day, the latest one will be used if applicable or the average of both observations will be used; if repeated measurements are on the same day, then the last measurement will be used.

Mapping visits may be handled case by case as well, if appropriate.

Early termination visits and unscheduled visits for safety data will be mapped in a similar way.

Some of the safety assessments are collected postdose in addition to the predose assessments (e.g. Neurological Examination at dosing visits, ECG, Vital Signs at Day1 visit, Serum PK at dosing visits). When windowing any predose assessments these should be the last available assessment prior to the dose. When windowing any postdose assessment they should correspond to the same dose as the predose assessment used for that visit. These summaries will present predose and postdose separately on by-visit summaries. If one of these assessments is collected at an unscheduled visit where there is no dosing, the assessment will be assigned as a predose assessment.

Descriptive statistics by visit for vital sign, ECG, Neurological examinations, lab and PK data will be summarized based on scheduled visits once unscheduled and early withdrawal visits are handled as mentioned above. All the postbaseline values will be used from both scheduled and unscheduled visits.

Unless being mapped to missing scheduled visits or specified, the assessments at unscheduled visits will not be used in the summary statistics but will be listed.

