4. STUDY OBJECTIVES AND ENDPOINTS

Part 1

Primary Objective	Primary Endpoint	
To evaluate the safety and tolerability of BIIB105 in participants with ALS or polyQ-ALS.	Incidence of AEs and SAEs in Part 1.	
Secondary Objective	Secondary Endpoints	
To assess the PK profile of BIIB105 in serum and CSF of participants with ALS or polyQ-ALS.	Serum and CSF concentrations of BIIB105 in Part 1. To evaluate the following serum PK parameters in Part 1:	
To evaluate the biomarker effect of BIIB105 in participants with ALS or polyQ-ALS.	Secondary biomarker measure: • Changes from baseline in plasma levels of NfL in Part 1	
Exploratory Objectives	Exploratory Endpoints	
To evaluate the PD effect of BIIB105 in participants with ALS or polyQ-ALS.	 Exploratory PD measure: Change from baseline in CSF levels of ATXN2 protein in Part 1. 	

Part 2

Primary Objective	Part 2 Primary Endpoint
To evaluate the long-term safety and tolerability of BIIB105 in participants with ALS or polyQ-ALS.	Incidence of AEs and SAEs in Part 2.

Integrated Part 1 and Part 2

Primary Objective	Primary Endpoint
To evaluate the long-term safety and tolerability of BIIB105 in participants with ALS or polyQ-ALS.	Incidence of AEs and SAEs during the BIIB105-treated period in Part 1 and/or Part 2.
Secondary Objective	Secondary Endpoints
To assess the long-term PK profile of BIIB105 in serum and CSF of participants with ALS or polyQ-ALS.	Serum and CSF concentrations of BIIB105 in Part 1 and Part 2. CSF trough PK concentration Serum PK concentration if available
To evaluate the long-term biomarker effect of BIIB105 in participants with ALS or polyQ-ALS, and, where relevant, to assess the impact of earlier initiation of BIIB105 (i.e., at start of Part 1) compared with delayed initiation of BIIB105 (i.e., at start of Part 2) on biomarkers.	• Changes from Part 1 baseline (Cohorts D1, D2) or Part 2 baseline (Cohorts A, B, C1, C2) in plasma levels of NfL

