8.1. Discontinuation of Study Treatment

A participant must permanently discontinue study treatment for any one of the following reasons:

- The participant becomes pregnant. Report the pregnancy according to the instructions in Section 12.4.1.
- The participant withdraws consent to continue study treatment.
- The participant experiences an AE that necessitates permanent discontinuation of study treatment.
- The participant experiences a medical emergency that necessitates unblinding of the participant's treatment assignment.
- The participant is unwilling or unable to comply with the protocol.
- At the discretion of the Investigator for medical reasons.
- At the discretion of the Sponsor.

The primary reason for discontinuation of study treatment must be recorded in the participant's CRF.

If a participant received a dose of study treatment, then he or she will be encouraged to complete all the scheduled safety evaluations during the ET Visit.

Participants who discontinue treatment are encouraged to remain in the study and continue protocol-required tests and assessments, where possible.

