- If the Day 1 of Part 2 falls into a window corresponding to a later analysis visit than Week 28, then all the remaining visits in Part 2 will be shifted accordingly. For example, if the Day 1 of Part 2 falls into the interval for Week 32, then the remaining visits in Part 2 will be labeled Week 36, Week 40 etc as follows.

Analysis Visit	Part 2 visit if Day 1=> Week 28	Part 2 visit if Day 1 => Week 32	Part 2 visit if Day 1 => Week 36
Week 28	Day 1	<skipped>	<skipped>
Week 30	Day 15	<skipped>	<skipped>
Week 32	Day 29	Day 1	<skipped>
Week 36	Day 57	Day 29	Day 1
Week 40	Day 85	Day 57	Day 29
Week 44	Day 113	Day 85	Day 57

CONFIDENTIAL

The information contained herein may not be used, disclosed, or published without the written consent of
Biogen MA Inc.

Week 48	Day 141	Day 113	Day 85
Week 52	Day 169	Day 141	Day 113
...

For endpoints with assessment every 12 weeks in Part 2, i.e. HHD, [REDACTED] their visits will be mapped as follows.

Analysis Visit	Part 2 visit if Day 1=> Week 28	Part 2 visit if Day 1 => Week 32
Week 28	Day 1	<skipped>
Week 30		<skipped>
Week 32		Day 1
Week 40	Day 85	Day 85
Week 52	Day 169	Day 169
Week 64	Day 253	Day 253
...

CONFIDENTIAL

The information contained herein may not be used, disclosed, or published without the written consent of
Biogen MA Inc.

Mapping visits may be handled case by case as well, if appropriate.

Visit mapping for other endpoints will follow the same logic as ALSFRS-R.

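### Early-termination and off-drug CSF PK samples are placed in dosing visits by calendar day, without regard to days since last dose

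*SAP*

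**What the plan says.** Part 1 SAP Section 3.1 sets the general rule: "Data from early termination visits and unscheduled visits will be assigned to an appropriate scheduled postbaseline visit using a windowing scheme". It then brings PK under that rule, stating that "lab and PK data will be summarized based on scheduled visits once unscheduled and early withdrawal visits are handled as mentioned above". Table 8, titled "Analysis Visit Windows for CSF PK/PD data", gives the CSF windows in study days. Two limits apply: within a window "data from the regular scheduled visit will be used for that visit", and unscheduled values otherwise enter summaries only when mapped to a missing scheduled visit or where specified. Mapping may also be handled case by case.

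For assessments taken both before and after dosing, with serum PK as a named example, the section adds: "If one of these assessments is collected at an unscheduled visit where there is no dosing, the assessment will be assigned as a predose assessment".

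The PK population (Part 1 SAP Section 3.4) requires one dose and one postdose measurement. Section 5.8 adds no condition on dosing status or time since dose. Protocol Section 8.1 says: "Participants who discontinue treatment are encouraged to remain in the study and continue protocol-required tests and assessments, where possible". Protocol Tables 1 and 2 schedule CSF sampling at the Final/ET visit.

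The final SAP (Part 2 and integrated), Section 3.1, windows the Day 214 and Day 259 follow-up visits of D1/D2 participants who do not enter Part 2 into four-weekly analysis weeks. It also shifts the visit sequence when Part 2 Day 1 falls late, and closes with: "Visit mapping for other endpoints will follow the same logic as ALSFRS-R". Its Section 5.8 confines the integrated D1/D2 PK summary to BIIB105-treated periods without saying when such a period ends. The protocol's integrated secondary endpoint (Section 4) is "CSF trough PK concentration".

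**The concern.** A concentration can be interpreted only against the time since the last dose. A study-day window controls for that only while dosing follows the schedule. Once a participant has stopped, the study day still points to a dosing visit but the sample is no longer a predose sample at the planned interval.

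CSF concentration is a secondary endpoint, and protocol Section 3.1.2 projects that four-weekly dosing holds steady-state exposure after the loading period. Off-drug samples can accumulate only as follow-up lengthens, so they affect the later visits most. A fall in the by-visit mean produced this way could be read as exposure not being maintained.

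**Working it through.** **1. Table 8 reproduced.** The note to the table gives lower bound = target − (target − previous target)/2 + 1, and upper bound = target + (next target − target)/2, or target + 14 for the last visit. For Day 113 in Cohorts D1/D2, lower = 113 − (113 − 85)/2 + 1 = 100 and upper = 113 + (141 − 113)/2 = 127. Both match. With half-days rounded down, all 15 postbaseline rows match. The windows depend on study day only.

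**2. Time since dose inside those windows.** Planned doses are on Days 1, 15, 29, 57 and 85 in all cohorts, and also on Days 113, 141 and 169 in D1/D2. Suppose the visit's own dose was not given and the last dose was at the preceding dosing visit:

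| Dosing visit | Nominal days since dose | Possible days since dose |
|---|---|---|
| Day 15 | 14 | 8-21 |
| Day 29 | 14 | 8-28 |
| Day 57; Days 85-169 in D1/D2 | 28 | 15-42 |
| Day 85 in A, B, C1, C2 | 28 | 15-31 |

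If an earlier dose was also missed, the gap is longer. With last dose Day 57 and ET on Day 105, study day 105 lies in 100-127, so the sample is reported at Day 113. Time since dose is 105 − 57 = 48 days, against 113 − 85 = 28.

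**3. Final SAP.** The window for week ww is ww×7 − 12 to ww×7 + 15, so Week 32 is Days 212-239 and Week 36 is Days 240-267. Take an early starter (120 mg in Part 1) whose last Part 1 dose was on Day 169:

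| Sample | Analysis week | Days since last dose |
|---|---|---|
| Follow-up Day 214 | 32 | 214 − 169 = 45 |
| Follow-up Day 259 | 36 | 259 − 169 = 90 |
| Part 2 Day 1, late roll-over | 32 | 212 − 169 = 43 to 239 − 169 = 70 |
| Part 2 Day 1, later roll-over | 36 | 240 − 169 = 71 to 267 − 169 = 98 |
| On-time early starter, Part 2 Day 29 or 57 | 32 or 36 | 28 |

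The last row counts active doses only: early starters receive BIIB105 on Part 2 Days 1 and 29 and placebo on Day 15. Participants given placebo in Part 1 have their PK baseline at the first 120 mg dose, so this comparison concerns early starters.

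**4. Illustrative size.** The documents give no terminal CSF half-life. Assume 30 to 150 days and a single exponential decline. Relative to a 28-day sample, a sample at g days is then 2^(−(g − 28)/half-life):
- g = 48: 2^(−20/30) = 0.63 to 2^(−20/150) = 0.91
- g = 45: 2^(−17/30) = 0.67 to 2^(−17/150) = 0.92
- g = 90: 2^(−62/30) = 0.24 to 2^(−62/150) = 0.75

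If a fraction p of a visit's samples has ratio r, the geometric mean is multiplied by r^p. Taking p = 5% purely as an example, the shortfall is 0.5-2.3% for 48-day samples and 1.4-6.9% for 90-day samples. The documents do not give p.

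**The case against.** Several limits are real. A scheduled value displaces an ET or unscheduled value in the same window, unscheduled values otherwise fill only missing visits, and mapping can be decided case by case. Table 8 keeps the post-treatment visits (Days 92, 130, 175, 176, 214 and 259) separate from dosing visits. An ET visit normally adds one CSF sample per participant. The PK analysis is descriptive, and individual concentrations are listed. Late roll-over in D1/D2 should be uncommon: Part 2 screening begins at Day 169, and the 42-day Part 2 screening extension in protocol Section 6.3.1 names only Cohorts A, B, C1 and C2. The final SAP's restriction to treated periods may be meant to remove follow-up samples.

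These points limit the frequency but do not remove the defect. The priority rule does not protect the ET case, because the scheduled visit is the one that is missing. The final SAP provides mapping columns for roll-over at Weeks 32 and 36, so it anticipates them. The treated-period wording cannot be applied without an end date.

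Four stronger readings are tempting but not supported:
- **That the SAPs report contaminated troughs.** Neither SAP uses the term. It belongs to the protocol's integrated CSF endpoint; the final SAP lists CSF PK concentration only.
- **That non-dosing serum samples are widely relabelled predose.** The sentence covers unscheduled visits only. No serum PK is scheduled at Final/ET or unscheduled visits, and the same paragraph says a predose value should be the last one before the dose. The serum windows are not visible.
- **That the SAP has a rule keeping off-drug participants' scheduled samples.** It is silent on this; their inclusion is inferred from the population definition.
- **That about 19% of Day 169 samples are off drug.** A reader might infer this from the 39 participants in the Part 1 SAP Section 2.3 power statement against 48 planned at 120 mg (9/48). That statement allows for dropout, and someone who has left gives no Day 169 sample.

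**Conclusion.** The concern holds for CSF on the stated rules. The Part 1 SAP can report an ET sample at 48 days post-dose as a visit whose nominal interval is 28 days. The final SAP can place samples 43 to 98 days post-dose in the same weeks as 28-day samples. The expected direction is downward at later visits. A mapped sample taken soon after a dose would push the other way, but that needs a dose given without its predose CSF, and both are planned at the same lumbar puncture.

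The time gaps follow from the planned dose days and printed windows. The roll-over figures also assume the Day 169 dose was given on schedule. The effect on a mean depends on the number of affected samples and on the CSF half-life, neither of which is in the documents, so no overall bias figure can be given. This is a cheap improvement to a descriptive secondary endpoint. It does not bear on the serum parameters, which come from separate non-compartmental analysis.

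**What to change.** In Section 5.8 of both SAPs:
- Restrict dosing-visit predose CSF and serum summaries to samples from participants who received the preceding scheduled active dose and were sampled within the visit window of the nominal 14- or 28-day interval.
- Do not map ET, unscheduled, follow-up or off-drug samples into dosing visits for PK. List them and plot them by actual days since last active dose.
- Define the end of the BIIB105-treated period, and either define trough for the integrated CSF endpoint or explain why the word was dropped.

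In Part 1 SAP Section 3.1, reconcile two pairs of sentences. One pair requires predose values to precede the dose yet labels non-dosing unscheduled samples predose. The other says all postbaseline values are used, yet limits unscheduled values to missing visits.

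The cost is SAP wording and one derived variable, days since last active dose, from dosing dates already recorded. The number of participants summarised at late visits will be slightly smaller.
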